6.1 Adverse Events (AEs)

An adverse event (AE) is any untoward occurrence in a subject, whether or not related to the product. An AE does not necessarily have to have a causal relationship with the study treatment. AEs include events not present at baseline and events that worsened if present at baseline.

Hospitalizations for pre-treatment conditions (e.g., elective cosmetic procedures) or surgeries that were planned prior to entry into the study are not considered adverse events.

Adverse events, regardless of causality, will be captured from the signing of the Informed Consent Form and for the duration of the subject's participation.

6.2 Serious Adverse Events (SAEs)

A **serious adverse event** (SAE) is any untoward medical occurrence that meets one or more of the following criteria according to federal regulations:

- a. results in death;
- b. is life-threatening (the subject was at risk of death at the time of the event. It does not refer to an event, which hypothetically might have caused death if it were more severe);
- c. results in persistent or significant disability or incapacity;
- d. requires inpatient hospitalization or prolongation of existing hospitalization;
- e. is a congenital anomaly or birth defect;

f. is considered an important medical event (may not be immediately life-threatening or result in death or hospitalization but may jeopardize the subject or may require intervention to prevent one of the outcomes listed in the definition above).

6.2 .1 SAE Reporting

An **Adverse Event or Suspected Adverse Reaction** is considered “serious” if, in the view of either the investigator or sponsor, it results in any of the following outcomes:

- Death;
- A life threatening adverse event; (Note: the term “life-threatening” as used here refers to an event in which the patient was at risk of death at the time of the event; it does not refer to an event which hypothetically might have caused death if it were more severe);
- In-patient hospitalization or prolongation of existing hospitalization;
- A persistent or significant disability/incapacity (substantial disruption of the ability to conduct normal life functions);
- A congenital anomaly/birth defect;
- Any “other” important medical event.

Important medical events that may not result in death, be life-threatening or require hospitalization may be considered Serious Adverse Events when, based on appropriate medical judgment, they may jeopardize the patient and may require medical or surgical intervention to prevent one of the outcomes listed in this definition.

Regardless of the above, any additional adverse events which the Principal Investigator considers significant should be immediately reported to Taro’s Drug Safety Department.

Any Serious Adverse Event, whether deemed drug-related or not, must be reported by the Investigator to the Taro’s Drug Safety Department by telephone **within 24 hours** after the Principal Investigator or Study Coordinator becomes aware of its occurrence. The Principal Investigator or the Principal Investigator’s Designee must complete a Serious Adverse Event (SAE) Form and email it to Taro’s Drug Safety Department, along with the patient’s Adverse Events Log and Concomitant Medications Log **within 24 hours** of notification of the event. When appropriate, Taro’s Drug Safety Department will notify the U.S. Food and Drug Administration (FDA) of drug related Serious Adverse Events.

Documentation of serious or unexpected adverse events and follow up information should be sent to Taro’s Drug Safety Manager within 24 hours from reporting the event by the Investigator. Following is the contact information:

Taro Drug Safety Manager:

[name], BSN,

Drug Safety Manager, Medical Affairs

Taro Pharmaceuticals U.S.A., Inc.

[contact] [name]

Email: [contact] and [contact]

Taro’s Drug Safety Department must notify FDA of fatal or life threatening adverse event as soon as possible but no later than 7 calendar days from reporting the event by the Investigator and within 15 calendar days for any other SAEs from the reporting of the event by Investigator.

The Sponsor-Investigator must inform all participating Investigators of any SAEs within 15 calendar days from reporting the event by the Investigator.

6.3 Pregnancy Reporting

The investigator will notify Taro Pharmaceuticals U.S.A. Inc. within 24 hours of discovery about any female subject who becomes pregnant after starting Topicort®. The investigator will follow the pregnancy and outcome. Any information gained will be shared with Taro Pharmaceuticals U.S.A. Inc. Female subjects who become pregnant while using Topicort® will be discontinued from study treatment.

7 INVESTIGATIONAL PRODUCT HANDLING

7.1 Investigational Product Receipt

At study initiation and as needed thereafter, Topicort® will be shipped to a responsible person at the investigator's institution, who will check the amount and condition of the drug, and maintain a record of this information. Taro Pharmaceuticals U.S.A. Inc. will instruct the Investigator on the return, disposal and/or destruction of investigational product and/or medical device materials if applicable.

7.2 Topicort Spray® Storage

Investigational product will be stored per the storage conditions identified on drug label. At the study site, all IP will be stored in a locked, safe area to prevent unauthorized access.

Records of the actual storage conditions during the period of the study will be maintained.

8 RECORD RETENTION

The investigator must retain these documents according to local laws or requirements. Essential documents include, but are not limited to, the following:

- Signed informed consent documents for all subjects;
- Subject identification code list, screening log (if applicable), and enrollment log;
- Record of all communications between the Investigator and the IRB/EC;
Composition of the IRB/EC;
- Record of all communications between the Investigator and Taro.
- List of Sub-investigators and other appropriately qualified persons to whom the Investigator has delegated significant study-related duties, together with their roles in the study, curriculum vitae, and their signatures;
- Copies of CRFs (if paper) and of documentation of corrections for all subjects;
- IP accountability records;

- Record of any body fluids or tissue samples retained;
- All other source documents (subject records, hospital records, laboratory records, etc);
- All other documents as listed in Section 8 of the ICH consolidated guideline on GCP (Essential Documents for the Conduct of a Clinical Trial).

The Investigator must notify Taro Pharmaceuticals U.S.A. Inc. if he/she wishes to assign the essential documents to someone else, remove them to another location or is unable to retain them for a specified period. The Investigator must obtain approval in writing from Taro Pharmaceuticals U.S.A. Inc. prior to destruction of any records. If the Investigator is unable to meet this obligation, the Investigator must ask Taro Pharmaceuticals U.S.A. Inc. for permission to make alternative arrangements. Details of these arrangements should be documented. All study documents should be made available if required by relevant health authorities. Investigator/Institution should take measures to prevent accidental or premature destruction of these documents.

8.1 Study Monitoring

The investigator will self-monitor all study records for accuracy, completeness, and compliance with the protocol and GCPs and federal regulations. All study records will be made available to Taro Pharmaceuticals U.S.A. Inc. representatives upon request. Study site facilities and study records will be made available to regulatory authorities' inspectors if an inspection takes place. The investigator will notify Taro Pharmaceuticals U.S.A. Inc. if this occurs.

8.2 Statistics

It is desired to have approximately n=20 subjects at randomization. Analysis will be performed by the Investigator of Investigator Global Assessment of scalp, Psoriasis Scalp Severity Index, Scalp Surface Area, PGA x BSA and patient reported outcomes. The Investigator will also analyze SAE's.

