Study Objectives	Primary Objective: To exploretheefficacyofTopicort®TopicalSprayatweeks4 and16 withrespectto Investigator GlobalAssessme nt(scalponly), Psoriasis ScalpSeverityIndex(PSSI) , andScalpSurfaceArea(SSA) Secondary Objectives: PGAxBSA,patient reportedoutcomes ,adverseevents
Study Design	A single center,observationalstudyof2 0subjectstoassess4weeksof therapy with Topicort® BIDand12weeks BIDontwoconsecutivedaysaweek patients with scalppsoriasis
Study Centers	PsoriasisTreatmentCenterofCentralNewJersey
Study Population	Adultmaleandfemalesubjectswithmoderatetoseverechronicplaque psoriasis
Main Inclusion Criteria	Subjectsmustmeetthefollowingcriteriatobenrolledinthisstudy: 1. Maleorfemaleadult \geq 18yearsofage; 2. Chronicscalppsoriasis \geq 30% 3. Investigator GlobalAssessment(scalponly) ofmildorgreater
Main Exclusion Criteria	Subjectswhomeetanyofthefollowingcriteriawillbeexcludedfrom participationinthisstudy: 1. Subjectswithnonplaquetypepsoriasis(e.g.guttate and erythrodermic). 2. Subjectswith<30%scalppsoriasis. 3. Useofprohibitedmedications duringstudyperiod.
Study Drug Dosage and Administration	Allpati entswillreceiveTopicort ® BIDfor4weeks. Afterweek4pat ientwillreceiveTopicort willreceiveTopicort® BIDontwo consecutivedaysaweek for12weeks . Patientswilltreatotherbodyareas affectedbyplaquepsoriasiswithTopicort®duringthestudyperiod(excludes face,groin,axilla)
Study Endpoints	Improvementafter 4and 16weeksof: InvestigatorGlobalAssessment(scalponly) PsoriasisScalpSeverityIndex Scalpsurfacearea Physician Global Assessment x Body Surface Area Pain,itching,scaling(scalponly) Scalpdex
Study Duration	16 weeks

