4. STUDY OBJECTIVE

To explore the effectiveness and safety of Topicort® Topical Spray for patients with scalp plaque psoriasis.

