5.5.1.4 Topicort Spray® Dosage Adjustments

If an SAE or an adverse event that is thought to be related to Topicort® and is not alleviated by symptomatic intervention, Topicort® will be discontinued. Subjects who permanently discontinue Topicort® therapy under this protocol should receive standard care of psoriasis treatment as prescribed by their physician.

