5.6.5 Physical Examination

A physical examination, including vital signs measurements (blood pressure and pulse), will be performed at each study visit. Any clinically significant abnormalities discovered during physical

examinations after the Screening / Baseline (if occurring on the same day) visit should be documented and evaluated as potential adverse events.

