5.6.11 Early Discontinuation Procedures

Subjects will be prematurely discontinued from the study under the following conditions:

1. Subject requests to withdraw from the study.
2. Subject is noncompliant with protocol schedule, restrictions, and/or requirements.
3. Subject experiences an adverse event that makes it difficult or intolerable for the subject to continue treatment, or increases risk to the subject, or interferes with the investigator's ability to clinically evaluate the progress of the subject's treatment.
4. Subject begins an unapproved concomitant therapy for psoriasis or another medical condition that may increase risk to the subject if continuing study treatment.
5. Subject cannot be reached / lost to follow-up.
6. The study investigator suspends or terminates the study.
7. Other unanticipated reason.

Any subject who prematurely discontinues the study should complete the week 16 (End of Study) assessments. Any subject who withdraws consent to participate in the study will be removed from further treatment and/or study observation immediately upon the date of request.

6 Adverse Events

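### Section 8.2 names SAEs as its only safety analysis, so the adverse-event secondary objective and the safety part of the study objective are not carried into the analysis

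*Combined protocol and SAP*

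**What the plan says.** The objectives cover safety in general. Section 4 reads "To explore the effectiveness and safety of Topicort® Topical Spray for patients with scalp plaque psoriasis". The Secondary Objectives row of the synopsis (spaces were lost in extraction) reads "PGAxBSA,patient reportedoutcomes ,adverseevents".

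Collection is equally broad. Section 6.1 states "Adverse events, regardless of causality, will be captured from the signing of the Informed Consent Form and for the duration of the subject's participation". The schedule in Appendix F marks adverse events at screening, enrollment and weeks 4, 8 and 16. Under Section 5.6.5, clinically significant examination findings "should be documented and evaluated as potential adverse events".

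The analysis text is narrower. Section 8.2 lists scalp IGA, PSSI, scalp surface area, PGA x BSA and patient-reported outcomes, and then adds "The Investigator will also analyze SAE's". Nothing else in that section concerns safety. Section 8.2.1 allows further procedures in a separate statistical plan, at the sponsor-investigator's discretion, and does not mention AEs.

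**The concern.** An objective needs an analysis that covers the data it refers to. Here the objective refers to adverse events, and the analysis section takes up only the serious ones.

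What would be lost is not trivial. Two provisions let an AE change a subject's course without being serious. Section 5.5.1.4 lists, as an alternative to an SAE, "an adverse event that is thought to be related to Topicort® and is not alleviated by symptomatic intervention" as a ground for stopping the drug. Section 5.6.11 ends participation where "Subject experiences an adverse event that makes it difficult or intolerable for the subject to continue treatment". A safety result confined to SAEs could leave both kinds of event uncounted, although they bear directly on how the treatment was tolerated.

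**Working it through.** No figure in the plan bears on this point, so the check is a comparison of the texts.

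**Step 1. Match each secondary objective to Section 8.2.**

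| Secondary objective (synopsis) | Named in Section 8.2 as |
|---|---|
| PGA x BSA | PGA x BSA |
| Patient-reported outcomes | Patient-reported outcomes |
| Adverse events | SAEs |

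Two of the three are carried over in full. The third is carried over in part.

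**Step 2. Is the SAE wording equivalent to AEs?** Not by the protocol's own definitions. Section 6.1 defines an AE as any untoward occurrence, related or not. Section 6.2 defines an SAE as one that meets at least one of six criteria (a to f). SAEs are therefore a subset, and what falls outside the named analysis is every AE that meets none of the six. Section 5.5.1.4 also uses the two terms side by side as different things.

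**Step 3. Does the omitted set include events the protocol treats as important?** Yes. Section 5.5.1.4 gives two alternatives for stopping the drug, an SAE or a related AE that does not resolve with symptomatic care; the second need not be serious. The AE ground in Section 5.6.11 depends on tolerability, risk or interference with evaluation, and does not mention seriousness.

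**Step 4. Does another section fill the gap?**

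- The Study Endpoints row of the synopsis opens with "Improvementafter 4and 16weeksof" and lists only efficacy and patient-reported measures. It has no safety endpoint.
- Section 6 covers definition, capture and reporting, not analysis.
- Section 8.2.1 permits a further plan but commits to nothing on AEs.

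None of these supplies an analysis of non-serious AEs.

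**Step 5. Are the data there?** Largely. All AEs are captured at every scheduled visit. Section 6.2.1 refers to an Adverse Events Log without listing its fields, and the diaries in Appendix G have a remarks column meant to include adverse events. Section 6 does not require relatedness, onset date or action taken for a non-serious AE. A count of subjects with any AE is therefore recoverable, but counts of related AEs and of AEs leading to discontinuation depend on what the log holds.

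**The case against.** The strongest reply is that this is a wording slip. Section 8.2 follows the order of the synopsis (PGA x BSA, patient-reported outcomes, then the safety term), so SAE may simply stand where AE was meant. That is plausible and cannot be settled from the documents. It would explain the mismatch, but the current text would still need the same correction.

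A second reply is that Section 8.2 says the investigator will *also* analyze SAEs, not *only* SAEs, and that the synopsis already fixes adverse events as an objective. This stands as a limit. A reader might infer that the plan rules out reporting non-serious AEs; it does not. The supportable claim is that Section 8.2 does not carry the objective forward.

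A third reply is that Section 8.2 gives no method for any outcome, so AEs are not singled out. True, and for that reason the risk of choosing a summary after seeing the data is not special to AEs. The difference is that each other outcome is at least named as the objective names it, whereas the safety outcome is named more narrowly.

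Finally, Section 6.2.1 requires any other AE that the principal investigator considers significant to be reported at once to the manufacturer's drug safety department. That limits the practical harm, but it is reporting of single cases and not analysis.

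**Conclusion.** Wrong as written, at low severity. Section 8.2 names a safety analysis narrower than the safety and adverse-event objectives and, followed literally, would omit non-serious AEs. The conclusion rests only on the protocol's own definitions of AE and SAE and on reading Section 8.2 as it stands; no event rate is assumed.

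The severity is low because the events are collected, a descriptive summary can still be made, no efficacy result is affected, and the study is a small exploratory one of about 20 subjects who all receive open-label treatment.

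A reader might infer that an SAE-only table would probably be empty, so that the study would have no safety result at all. The documents do not support this: they give no SAE rate, and SAEs are reported whatever their cause. Nor would a wide confidence interval around zero events in 20 subjects measure the defect. That width comes from the sample size and would be the same after the correction.

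**What to change.** In Section 8.2, replace the reference to SAEs with *all adverse events and SAEs*, and add that they are summarised descriptively as number and percent of subjects who received at least one dose with:

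- any AE;
- any AE judged related to study drug;
- any AE leading to discontinuation;
- any SAE.

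List events before the first dose separately. Capture starts at consent, and Section 5.6.2 allows screening up to 30 days before dosing, so such events can occur.

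A split by treatment period is not needed to meet the objective. It would also require a rule for the extension days 29 to 32 in the Appendix G diary, which belong clearly to neither period.

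The cost is a few sentences, one more descriptive table, and making sure the AE log records relatedness, onset date and action taken for non-serious AEs. No visit or efficacy analysis changes.

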8.2.1 Additional Statistical Considerations

Additional statistical procedures may be detailed in and performed according to a separate statistical plan at the discretion of sponsor-investigator.

REFERENCES

2. Camp RDR. Psoriasis. In: Champion RH, Burton JL, Burbs DA, Breathnach SM, eds. *Textbook of Dermatology*, 6th Edition. 1998;2:1589- 1649.
5. Keegan B. Desoximetasone 0.25% spray for the relief of scaling in adults with plaque psoriasis. *Journal of Drugs in Dermatology* 2015 Aug pp 611-615

8. APPENDICES**Appendix A****Investigator Global Assessment
(Scalp Only)****0 – Clear**

No signs of psoriasis. Post-inflammatory hyperpigmentation may be present

1 – Almost Clear

Normal to pink coloration of lesions, no thickening, no minimal focal scaling

2 – Mild disease

Pink to light red coloration; just detectable to mild thickening, predominately fine scaling

3 – Moderate disease

Dull bright red, clearly distinguishable erythema, clearly distinguishable to moderate thickening, moderate scaling

4 – Severe disease

Bright to deep dark red coloration, severe thickening with hard edges, severe/courses scaling covering almost all or all lesions

Appendix B**Psoriasis Scalp Severity Index (PSSI) and Scalp Surface Area (SSA)****Psoriasis Scalp Severity Index (PSSI) and Scalp Surface Area (SSA)**

Erythema (E)	Thickening	Scaling	Scalp Surface Area Score
	Plaque elevation	Desquamation (D)	SSA score
	Induration (I)		
0 None	0 None	0 None	1 <10 %
1 Slight	1 Slight	1 Slight	2 10-29%
3 Moderate	3 Moderate	3 Moderate	3 30-49%
4 Severe	4 Severe	4 Severe	4 50-69%
5 Very Severe	5 Very Severe	5 Very Severe	5 70-89%
			6 90-100%

Erythema	Thickening	Scaling	Scalp Surface Area Score
     1 2 3 4 5	     1 2 3 4 5	     1 2 3 4 5	     1 2 3 4 5 6

Scalp Surface Area

Record 0-100%

 %

Total PSSI score _____

PSSI SCORE = SUM OF SCORES FOR ERYTHEMA, THICKENING AND SCALING MULTIPLIED BY SCALP SURFACE AREA

(scores range from 0-72)

Appendix C

Physician's Global Assessment

Static Physician's Global Assessment (sPGA)

Score	Category	Description
0	Clear	Plaque elevation = 0 (no elevation over normal skin) Scaling = 0 (no evidence of scaling) Erythema = 0 (except for residual hyperpigmentation/hypopigmentation)
1	Almost Clear	Plaque elevation = ± (possible but difficult to ascertain whether there is a slight elevation above normal skin) Scaling = ± (surface dryness with some desquamation) Erythema = ± (faint, diffuse pink or slight red coloration)
2	Mild	Plaque elevation = slight (slight but definite elevation, typically edges are indistinct or sloped) Scaling = fine (fine scale partially or mostly covering lesions) Erythema = mild (light red coloration)
3	Moderate	Plaque elevation = marked (marked definite elevation with rough or sloped edges) Scaling = coarser (coarser scale covering most or all of the lesions) Erythema = moderate (definite red coloration)
4	Severe	Plaque elevation = marked (marked elevation typically with hard or sharp edges) Scaling = coarser (coarse, non tenacious scale predominates covering most or all of the lesions) Erythema = severe (very bright red coloration)

[figure not shown]
Appendix D

Subject Assessment of Pain, Itching and Scaling

Select the number that best describes your scalp psoriasis symptoms during the past 24 hours

Please mark (x) one box only

Pain: Overall, how severe was your psoriasis-related pain over the past 24 hours?

Itching: Overall, how severe was your psoriasis-related itch over the past 24 hours?

Scaling: Overall, how severe was your psoriasis-related scaling over the past 24 hours?

Appendix E

CONFIDENTIAL

Scalpdex

These questions concern your feelings over the past 4 weeks about **your scalp condition**. Check the answer that comes closest to the way you have been feeling.

**HOW OFTEN DURING THE PAST 4 WEEKS
DO THESE STATEMENTS DESCRIBE YOU?**

	NEVER	RARELY	SOMETIMES	OFTEN	ALL THE TIME
1. My scalp hurts	 1	 2	 3	 4	 5
2. My scalp condition makes me feel depressed	 1	 2	 3	 4	 5
3. My scalp itches	 1	 2	 3	 4	 5
4. I am ashamed of my scalp condition	 1	 2	 3	 4	 5
5. I am embarrassed by my scalp condition	 1	 2	 3	 4	 5
6. I am frustrated by my scalp condition	 1	 2	 3	 4	 5
7. I am humiliated by my scalp condition	 1	 2	 3	 4	 5
8. My scalp condition bleeds	 1	 2	 3	 4	 5
9. I am annoyed by my scalp condition	 1	 2	 3	 4	 5
10. I am bothered by the appearance of my scalp condition	 1	 2	 3	 4	 5
11. My scalp condition makes me feel self-conscious.	 1	 2	 3	 4	 5
12. I am bothered that my scalp condition is incurable.	 1	 2	 3	 4	 5
13. My scalp condition affects how I wear my hair (hairstyle, hats)	 1	 2	 3	 4	 5
14. I am bothered by people's questions about my scalp condition.	 1	 2	 3	 4	 5
15. My scalp condition affects the color of clothes I wear.	 1	 2	 3	 4	 5
16. I am bothered by the persistence/reoccurrence of my scalp condition.	 1	 2	 3	 4	 5
17. I feel stressed about my scalp condition.	 1	 2	 3	 4	 5
18. Caring for my scalp condition is inconvenient for me.	 1	 2	 3	 4	 5
19. I feel that my knowledge for caring for my scalp is adequate	 1	 2	 3	 4	 5
20. The cost of caring for my scalp condition bothers me.	 1	 2	 3	 4	 5
21. My scalp condition makes my daily life difficult.	 1	 2	 3	 4	 5
22. My scalp condition makes me feel different from others.	 1	 2	 3	 4	 5
23. My scalp condition makes it hard to go to the hairdresser/barber.	 1	 2	 3	 4	 5

